### 13.4 Reporting of PK Parameters

The PK parameters will be summarized. In addition to standard univariate statistics, the coefficient of variation, geometric mean and geometric standard deviation will be added.

**Table TTT. PK Parameters** 

### 14 Exploratory Analyses

Exploratory analysis will be done on the Safety set.

#### 14.1 Endpoints

The endpoints are:

Serum and urine OA-related biomarkers (exploratory proteomic research of 4P004 efficacy related biomarkers) at D1 (T0-15min, 8h, 24h) and D8.

The exploratory endpoint will be analyzed separately, and the related data will not be included in the SDTM/ADaM datasets.

### 15 Reporting Conventions

The following reporting conventions will be adopted for the SAP. These conventions will enhance the review process and help to standardize presentation with common notations.

### 15.1 General Reporting Conventions

Legends will be used for figures with more than one variable or item displayed.

All date values will be presented as YYYY-MM-DD (e.g., 2001-08-29) format.

As a general rule, percentages will be presented with one decimal digit, but can be presented with no decimal digit for table width requirements.

#### **15.2 Population Summary Conventions**

The biomarker concentration in serum determined at each sampling time point should be presented on the original scale for each subject participating in the study.

Population(s) identified in all TFL titles as "All Subjects", "Safety Population" or "PK Population".

#### 16 References

ICH Guidance Topic E9 "Statistical Principles for Clinical Trials"

# 17 Tables, Figures & Listings in CSR Section 14

The following tables will be included in the report either in the text or in a dedicated chapter reporting all tables but not included in the text.

Туре	Number	Title	Population
Table	1.1	Participant disposition	All
Table	1.2	Deviations by Category	Safety
Listing	1.2.1	Major Deviations	Safety
Table	1.3	Demographics and Baseline Characteristics	Safety
Table	1.4	Other Baseline Characteristics	Safety
Table	1.5.1	Pain killers started and ended before treatment	Safety
Table	1.5.2	Other medications started and ended before treatment	Safety
Table	1.6	Medical History by SOC	Safety
Table	2.1	Pain killers started before treatment and continuing at IMP injection	Safety
Table	2.2	Pain killers started during treatment	Safety
Table	2.3	Other medications started before treatment and continuing at IMP injection	Safety
Table	2.4	Other medications during treatment	Safety
Table	3.1	Overview of TEAEs	Safety
Table	3.1.1	TEAEs by SOC and PT	Safety
Table	3.1.2	TEAEs by SOC, PT and Toxicity Grade	Safety
Table	3.1.3	TEAEs by SOC, PT and Relationship to Study Drug	Safety
Table	3.2	Treatment-Emergent AESIs by SOC and PT	Safety
Table	3.2.1	Treatment-Emergent AESIs by SOC, PT and Toxicity Grade	Safety
Listing	3.2.2	Treatment-Emergent AESIs	Safety
Table	3.3	Injection Site Reactions	Safety
Listing	3.4	Serious Adverse Events	Safety
Listing	3.5	Deaths	Safety
Table	4.1	Target Knee Pain from Pre-Dose to 24h Post-Dose	Safety
Table	4.2	Target Knee Pain from Visit 2 to End of Study	Safety
Table	4.3	Target Knee Pain from Visit 2 to Day 8	Safety
Table	5.0	Weight over Time	Safety
Table	5.1	Systolic Blood Pressure over Time	Safety
Table	5.2	Diastolic Blood Pressure over Time	Safety
Table	5.3	Heart Rate over Time	Safety
Table	6.1	ECG: Heart Rate over Time	Safety
Table	6.2	ECG: PR over Time	Safety
Table	6.3	ECG: QRS over Time	Safety
Table	6.4	ECG: QT over Time	Safety
Table	7.1	Hematology over Time	Safety
Table	7.1.1	Hematology PCSA over Time	Safety
Table	7.2	Chemistry over Time	Safety
Table	7.2.1	Chemistry PCSA over Time	Safety
Table	7.3	Glycemia over Time	Safety
Table	8.1	Plasma Concentrations over Time	PK
Figure	8.1.0.3	Plasma Concentrations over Time by Subject -	PK
Figure	8.1.1	Plasma Concentrations over Time by Subject -	PK
Figure	8.1.2	Plasma Concentrations over Time by Subject -	PK
Figure	8.1.3	Plasma Concentrations over Time by Subject -	PK
Table	8.2	PK Parameters	PK

# 18 Listings in CSR Section 16.2

The following listings will be included in section 16.2 of the CSR.

Туре	Number	Title	Population
Listing	16.2.1	Demographics and Disposition	Safety
Listing	16.2.2	Prior and Concomitant Medications	Safety
Listing	16.2.3	Medical History	Safety
Listing	16.2.4	Serology	Safety
Listing	16.2.5	Knee X-Ray and Kellgren-Lawrence Grade	Safety
Listing	16.2.6	Failed Inclusion/Exclusion Criteria	Safety
Listing	16.2.7	IMP Injection	Safety
Listing	16.2.8	Deviations	Safety
Listing	16.2.9	Adverse Events	Safety
Listing	16.2.10	Knee Pain Assessments	Safety
Listing	16.2.11	Height, Weight and BMI	Safety
Listing	16.2.12	Vital Signs	Safety
Listing	16.2.13	ECG	Safety
Listing	16.2.14	Hematology	Safety
Listing	16.2.15	Chemistry	Safety
Listing	16.2.16	Glycemia	Safety
Listing	16.2.17	Exploratory Sample Collection	Safety
Listing	16.2.18	Plasma Concentrations	Safety
Listing	16.2.19	PK Parameters	Safety
Listing	16.2.20	Visits	Safety
Listing	10.2.20	VISITS	Sarety

# 19 Potentially Clinically Significant Abnormalities

Potentially clinically significant abnormality (PCSA) values are defined as abnormal values considered medically important by the Sponsor, according to predefined criteria/thresholds based on literature reviews and defined by the Sponsor for clinical laboratory tests, vital signs, and ECG parameters.

When possible, PCSA will be computed at baseline or before.

Parameter	PCSA	Comments
Chemistry		
AST or ALT	> 3 ULN	Guidance for Industry Drug-Induced Liver Injury FDA, 2009
Potassium	< 3 mmol/L or ≥ 5.5 mmol/L	
CLcr (mL/min) (Estimated creatinine clearance based on the Cokcroft Gault equation)	< 15 (end stage renal disease) ≥ 15 - < 30 (severe decrease in GFR) ≥ 30 - < 60 (moderate decrease in GFR)	FDA draft Guidance 2020 Pharmacokinetics in Patients with Impaired Renal Function Study Design, Data Analysis, and Impact on Dosing
Amylasemia	≥ 1.5 ULN	
Glycemia	< 70 mg/dL	DSMB
Hematology		
RBC	≥ 6 Tera/L	
Hb	≤ 115 g/L (Male); ≤ 95 g/L (Female) ≥ 185 g/L (Male); ≥ 165 g/L (Female) Decrease from Baseline ≥ 20 g/L	Criteria based upon decrease from baseline are more relevant than based on absolute value.
WBC	< 3.0 Giga/L (Non-Black) < 2.0 Giga/L (Black) ≥ 16.0 Giga/L	
Lymphocytes	> 4.0 Giga/L	
Neutrophils	< 1.5 Giga/L (Non-Black); < 1.0 Giga/L (Black)	International Consensus meeting on drug- induced blood cytopenias, 1991. FDA criteria.
Monocytes	> 0.7 Giga/L	
Basophils	> 0.1 Giga/L	
Eosinophils	> 0.5 Giga/L	Harrison- Principles of internal Medicine 17th Ed., 2008
Platelets	< 100 Giga/L ≥ 700 Giga/L	International Consensus meeting on drug- induced blood cytopenias, 1991.
Vital Signs		
HR (bpm)	≤ 50 + decrease from baseline ≥ 20 ≥ 120 + increase from baseline ≥ 20	
SBP (mmHg)	≤ 95 + decrease from baseline ≥ 20 ≥ 160 + increase from baseline ≥ 20	
DBP (mmHg)	≤ 45 + decrease from baseline ≥ 10 ≥ 110 + increase from baseline ≥ 10	
ECG		
HR (bpm)	< 50 < 50 + decrease from baseline ≥ 20 > 100 > 100 + increase from baseline ≥ 20	
PR (ms)	> 200 > 200 + increase from baseline ≥ 25%	
QRS (ms)	> 110 > 110 + increase from baseline ≥ 25%	
QT (ms)	> 500

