## 3.2 Endpoints

#### 3.2.1 Primary endpoints

- Number of Adverse events (AEs), serious AEs (SAEs) (Common Terminology Criteria Adverse Events [CTC-AE]) from ICF signature to D29, including target knee pain and tenderness, erythema, swelling, local pain at injection site.
- Vital signs from D-7 to D8, ECG from D-7 to D1: Mean change, number of Potentially Clinically Significant Abnormality (PCSA), Percentage of participants with PCSA
- Laboratory changes (Red Blood Cells (RBC), White Blood Cells (WBC), Hemoglobin (Hb), platelets, alanine transaminase (ALT), aspartate transaminase (AST), glycemia, amylasemia, creatinin clearance) from D-7 to D8: Mean changes number of PCSA, Percentage of participants with PCSA.

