### 9 General Principles for Statistical Analysis

Data will be summarized using classical descriptive statistics for the following groups:

- pooled placebo (i.e. participants receiving placebo in any cohort),
- each 4P004 dose level,
- unplanned doses if any (see below),
- 4P004 overall

A group "All" (Placebo + 4P004 overall) will be added if explicitly mentioned.

Categorical data will be presented using counts and percentages of subjects, while continuous variables will be presented using the mean, standard deviation, median, minimum, maximum, and number of observations with non-missing values. The coefficient of variation [%CV] will be provided for PK parameters.

The safety evaluation will be based upon the review of the individual values and descriptive statistics. No statistical significance tests will be performed on safety data.

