### 9.4 Derived and Computed Variables

For any variable, the baseline value is defined as the last observation before IMP injection.

The time will be split into 3 periods (epochs):

- before treatment (screening)
- during treatment (from IMP injection to 7 days after IMP injection date)

after treatment

The following PK parameters will be calculated from measured plasma concentrations for each participant:

- Maximum observed concentration (Cmax)
- Time of maximum observed concentration (Tmax)
- Area under the curve (AUC0-t)
- Terminal Half-life (T1/2)

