#### **Table TTT. Weight over Time**

#### 12.5 Vital Signs

The vital signs are systolic blood pressure, diastolic blood pressure and heart rate. They are measured as follows:

Visit	Timepoint
Screening	-
Visit 2	Pre-Dose
	1h Post-Dose
	2h Post-Dose
	4h Post-Dose
	8h Post-Dose
	12h Post-Dose
	24h Post-Dose
Visit 3	_

The following will be presented for each vital sign:

- value (mean, SD, etc.)
- absolute change from baseline (mean, SD, etc.)
- PCSA (frequencies and percentages)

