### 12.7 Clinical safety laboratory assessment

The Hematology and Chemistry parameters are collected at Screening and Visit 3.

They are:

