**Table TTT. Hematology over Time** 

	Placebo	4P004	4P004	4P004	4P004	4P004
	(pooled)					(pooled)
	(N=XX)	(N=XX)	(N=XX)	(N=XX)	(N=XX)	(N=XX)
Erythrocytes (tera/L)						
Baseline						
Value						
n	XX	XX	XX	XX	XX	XX
mean (SD)	XX (XX)					
()						
PCSA						
≤ 95 + decrease from baseline ≥ 20	XX (XX.X%)					
≥ 160 + increase from baseline ≥ 20	XX (XX.X%)					
No PCSA	XX (XX.X%)					
Visit 3						
Value						
n	XX	XX	XX	XX	XX	XX
mean (SD)	XX (XX)					
()						
Change from BL						
n	XX	XX	XX	XX	XX	XX
mean (SD)	XX (XX)					
()						
PCSA						
≤ 95 + decrease from baseline ≥ 20	XX (XX.X%)					
≥ 160 + increase from baseline ≥ 20	XX (XX.X%)					
No PCSA	XX (XX.X%)					
()						

For parameters with defined PCSA, a table with PCSA only will be produced:

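### For PCSA limits with no change-from-baseline condition, the SAP tables count persisting abnormalities after dosing and do not separate them from new ones

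*SAP*

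**What the plan says.** Protocol 3.2.1 makes "Percentage of participants with PCSA" a primary endpoint for vital signs, ECG and laboratory values. For laboratory values the wording is "from D-7 to D8: Mean changes number of PCSA, Percentage of participants with PCSA". It does not ask for new or treatment-emergent PCSAs.

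SAP 9 states that "Categorical data will be presented using counts and percentages of subjects", and SAP 9.4 that "the baseline value is defined as the last observation before IMP injection". The templates in SAP 12.5 and 12.7 show PCSA counts and percentages at each timepoint, under columns headed by the arm N. SAP 12.7 adds: "For parameters with defined PCSA, a table with PCSA only will be produced". The haematology template has a Baseline block and a Visit 3 block, each a separate count, and chemistry is to follow the same layout. ECG (SAP 12.6) and glycemia (SAP 12.7) use the vital-signs template, whose Baseline block shows values only and no PCSA lines.

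SAP 19 says of baseline status only that "When possible, PCSA will be computed at baseline or before". The table list in SAP 17 has no shift table, and no section defines a treatment-emergent PCSA. For adverse events, SAP 12.2.1 does separate pre-treatment from treatment-emergent events.

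**The concern.** A post-dose PCSA percentage will be read as an effect of the dose. If the criterion is an absolute limit, a participant who was beyond it before the injection and stays beyond it is counted in the post-dose row like a participant who crossed it after the injection. Two separate counts, one before and one after, do not show whether they concern the same people.

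With six participants per dose level, one persisting case can create an apparent dose effect, and one in placebo can hide one. No significance tests are planned, so the descriptive table is the whole analysis of this endpoint. The SAP accepts the principle for haemoglobin: its comment in section 19 says that criteria based on a decrease are more relevant than absolute ones. Most of the other laboratory limits stay absolute.

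**Working it through.** The plan states no figure to reproduce: the sample size has no power basis. The check has three steps.

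**1. Which criteria are exposed.** Counting sex- or race-specific limits as one criterion, and AST/ALT as one, SAP 19 contains:

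| Group | Absolute only | Needs a change from baseline |
|---|---|---|
| Chemistry | 8 | 0 |
| Haematology | 12 | 1 (Hb decrease) |
| Vital signs | 0 | 6 |
| ECG | 5 | 4 |
| Total | 25 | 11 |

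For haematology and chemistry, SAP 12.7 says "The Hematology and Chemistry parameters are collected at Screening and Visit 3", so the baseline sample is the screening sample. Eight of the 25 absolute criteria then cannot be met at baseline without an eligibility deviation under Protocol 5.1: AST/ALT, three creatinine-clearance bands, amylase, low Hb, low WBC and low platelets. That leaves 25 − 8 = 17:

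- 11 with no entry limit: low and high potassium, RBC, high Hb, high WBC, high platelets, lymphocytes, neutrophils, monocytes, basophils, eosinophils.
- 6 covered by an entry criterion (I8 or I13) but with a new pre-dose value on D1 as baseline: glycemia below 70 mg/dL, and absolute ECG HR low, HR high, PR, QRS and QT.

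**2. What two separate counts can tell.** With b cases at baseline and v after dosing among n participants, the number of new cases lies between max(0, v − b) and min(v, n − b).

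- b = 1, v = 1, n = 6: 0 to 1 new
- b = 1, v = 2, n = 6: 1 to 2 new
- b = 2, v = 2, n = 6: 0 to 2 new

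If b = 0, all v cases are new. If v = 0, none are. The ambiguity arises only when both counts are non-zero.

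**3. Size.** Planned denominators (SAP 5.2 and 7) are 6 per dose level, 4 × 2 = 8 pooled placebo and 4 × 6 = 24 pooled active.

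| Situation | As planned | New, among those free at baseline |
|---|---|---|
| Dose level, 1 persisting | 1/6 = 16.7% | 0/5 = 0% |
| Dose level, 1 persisting + 1 new | 2/6 = 33.3% | 1/5 = 20.0% |
| Pooled placebo, 1 persisting | 1/8 = 12.5% | 0/7 = 0% |
| Pooled placebo, 1 persisting + 1 new | 2/8 = 25.0% | 1/7 = 14.3% |
| Pooled active, 1 persisting | 1/24 = 4.2% | 0/23 = 0% |

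The ninth cohort 3 participant (SAP 9.3) may shift one denominator: 1/7 = 14.3% in a dose arm, or 1/9 = 11.1% in pooled placebo.

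How often this could arise depends on a prevalence that the documents do not give. Assuming that 2%, 5% or 10% of participants meet a given limit before dosing, the chance of at least one in an arm of 6 is 1 − (1 − p)^6 = 11%, 26% or 47%. These are upper bounds for carry-over, which also needs the abnormality to be present again after dosing.

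**The case against.** The strongest reply is that the information is not lost. SAP 19 has baseline status derived where possible, and the haematology and chemistry layout shows a baseline count beside Visit 3. Protocol 10.1.4 has laboratory PCSA results listed individually, and SAP 18 lists all ECG, haematology, chemistry and glycemia data. With six per arm, a reviewer can trace each case. On the assumed prevalences, an arm has no baseline case for a given parameter with probability 89% to 53%, and every post-dose case is then new. All of this stands, so it would be wrong to infer that new and persisting cases cannot be told apart at all. The limit lies in the summary tables, which are where a percentage endpoint is read.

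Four other stronger readings do not hold:

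- **That pre-dose values count as endpoint events because the laboratory window opens at D-7.** The same endpoint asks for mean changes, which need pre-dose data, and the templates keep Baseline apart from post-dose rows.
- **That the comparison of arms is biased in a known direction.** Assignment to active or placebo is randomised within each cohort. Dose levels are successive cohorts, but nothing in the documents suggests that pre-existing abnormalities rise or fall with dose. This is chance imbalance, large because arms are small.
- **That risks multiply across parameters.** Treating six parameters as independent would give 1 − (1 − p)^36 = 52% to 98% for p of 2% to 10%. Several of the exposed criteria are WBC and its components, which are not independent, and each parameter has its own table row.
- **That dose decisions rest on these percentages.** Protocol 4.6.1 gives dose-limiting toxicities their own criteria, and the ECG stopping rule needs an event judged related to the product.

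ECG HR, PR and QRS also have threshold-plus-change categories that flag worsening, and entry criteria I8 and I13 make a D1 ECG or glycemia PCSA less likely. Both points reduce the ECG and glycemia part of the concern without removing it.

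**Conclusion.** The concern holds for the 17 absolute-only criteria in SAP 19 that can be met before dosing. For these, the plan defines neither a treatment-emergent PCSA nor a baseline-by-post-dose table, so a persisting abnormality enters a primary safety percentage after dosing. One such participant is worth 16.7 points at a dose level and 12.5 points in pooled placebo, at the planned denominators. The gap is widest for ECG and glycemia, whose template shows no PCSA count at baseline; for vital signs that omission is harmless, because each of those criteria already requires a change.

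The counts of criteria and the percentages follow from the documents. How often the problem will occur does not, since it rests on an assumed prevalence and on persistence. The consequence is moderate: the analysis is descriptive and individual data are listed. It is still worth correcting before the tables are run, because the data needed are already collected. The documents do not support replacing the protocol's percentage, which is defined over participants with a PCSA and stays valid as such.

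**What to change.** For the criteria with no change-from-baseline condition, add a row headed *new PCSA* to the ECG tables (6.1 to 6.4), the haematology and chemistry PCSA tables (7.1.1 and 7.2.1) and the glycemia table (7.3). Define it as present after injection and absent at baseline, with the participants without that PCSA at baseline as denominator. A baseline-by-post-dose cross-table would serve equally well. Where there are several post-dose timepoints, as for glycemia, give the row for each scheduled timepoint and for any post-dose time.

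Keep the all-participant percentage beside it as the protocol-defined endpoint, so that worsening of a baseline abnormality stays visible and the primary endpoint is unchanged. State in the SAP that dose effects will be interpreted from the new-PCSA row.

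The cost is SAP wording and table programming, with no new data. Tables become slightly longer and denominators will vary by parameter, so each row should print its own.

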## **5 STUDY POPULATION**

#### 5.1 Inclusion criteria

- I1. Participants who have the capacity to give informed consent and who are willing to comply with all study related procedures and assessments (consent via legally authorized representative will not be accepted),
- 12. Ambulatory participants, agreeing a 24-hour hospitalization,
- I3. Participants between 18 and 80 years of age,
- I4. Female participant of childbearing potential (WOCBP), must use contraceptive consistent with local regulations regarding the methods of contraception for those participating in clinical studies (see section 11.4) for at least 5 days following IMP injection, and must have a negative urine pregnancy test done within 24h before randomization,
- I5. Male participants (whose partners are of childbearing potential) must consent to use methods of contraception consistent with local regulations regarding the methods of contraception for those participating in clinical studies (see section 11.4), for at least 90 days following IMP injection,
- I6. Participants with knee osteoarthritis, KL 2-4 of their target knee (defined at screening as the knee with greater pain based on the participant's evaluation and the investigator's clinical judgment),
- 17. X-ray of the target knee within 6 months (if not, to be performed before randomization),
- I8. ECG within normal range,
- I9. WBC (white blood cell count)  $> 3500/\mu L$ ,
- I10. Hemoglobin > 12 g/dL,
- I11. Platelets  $> 100,000/ \mu L$ ,
- I12. Creatinine clearance (CrCl) > 60 mL/min,
- I13. Glycemia within normal range,
- I14. AST, ALT < 1.5 upper limit of normal (ULN),
- I15. Amylasemia < 1ULN,
- I16. Negative tests for COVID-19 (if required by the standard practice on site), HIV, HbsAg and hepatitis C Ab (Determination of HIV and hepatitis status can be based on participant-reported medical history, available medical records, and the most recently available laboratory results for the participant [tests performed within the previous 12 months]).

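### SAP 19 scores creatinine clearance only by absolute bands below 60 mL/min, which is also the entry limit, so whether a fall counts as a PCSA depends on the starting value

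*SAP*

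**What the plan says.** - **Endpoint.** Protocol 3.2.1 names creatinine clearance among the primary laboratory parameters: "glycemia, amylasemia, creatinin clearance) from D-7 to D8: Mean changes number of PCSA, Percentage of participants with PCSA".
- **Entry.** Inclusion criterion I12 requires "Creatinine clearance (CrCl) > 60 mL/min".
- **PCSA definition.** SAP 19 gives estimated clearance (Cockcroft-Gault) three absolute bands: "< 15 (end stage renal disease) ≥ 15 - < 30 (severe decrease in GFR" and then "≥ 30 - < 60 (moderate decrease in GFR". The comment column attributes them to a guidance on pharmacokinetics in patients with impaired renal function. The row has no change-from-baseline criterion.
- **Other rows of SAP 19.** Haemoglobin has a standalone change criterion, "Decrease from Baseline ≥ 20 g/L", with the comment "Criteria based upon decrease from baseline are more relevant than based on absolute value". Vital signs, PR and QRS have criteria that combine an absolute limit with a change from baseline. For PR and QRS the change is an increase of at least 25%.
- **Sampling.** SAP 12.7 has chemistry at Screening and Visit 3 only. Baseline is the last value before injection (SAP 9.4), so for clearance it is the screening value.

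**The concern.** The bands classify a level of renal function. The endpoint is meant to detect an abnormality arising after one injection. Because the top band begins exactly where eligibility ends, no participant who met I12 can be a PCSA at baseline, and every post-dose flag is a first crossing of 60. What triggers the flag is the distance from 60 at entry, not the size of the loss.

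For most other laboratory tests the PCSA limit is set apart from the entry limit. Transaminases enter below 1.5 ULN and are flagged above 3 ULN. Amylase enters below 1 ULN and is flagged from 1.5 ULN. White cells enter above 3500/µL and are flagged below 3.0 Giga/L (2.0 for Black participants). Clearance has neither such a margin nor a change criterion. Platelets share this layout.

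A fall in clearance is worth counting well here. Protocol 2.3 reports nausea in 5 participants and vomiting in 4 in cohort 3. With 6 active participants per dose, one flag given or withheld moves a dose-level percentage by 1/6, about 17 points.

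**Working it through.** The plan states no figure on this point, so there is none to reproduce. The inputs from the documents are the limit of 60 mL/min (SAP 19 and I12) and 32 participants (Protocol 1.1). The baseline distributions and the within-person CV are assumptions.

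**1. Largest fall that is not counted.** From baseline b, a value is counted only if it is below 60, so the largest uncounted fall is (b - 60)/b.

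| Baseline (mL/min) | Largest uncounted fall |
|---|---|
| 61 | 1.6% |
| 65 | 7.7% |
| 80 | 25.0% |
| 90 | 33.3% |
| 100 | 40.0% |
| 120 | 50.0% |

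A 2% fall counts only if 0.98b < 60, that is, for b below 61.2 (61 falls to 59.78; 62 falls to 60.76 and is not counted).

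**2. Share of participants in whom a uniform true fall f is counted.** A fall f is counted if b < u, where u = 60/(1 - f): 85.7 for 30%, 100 for 40%, 120 for 50%. With baseline N(m, s) truncated above 60, the share is [Φ((u - m)/s) - Φ((60 - m)/s)] / [1 - Φ((60 - m)/s)].

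Example, N(80,20) and f = 30%: (0.612 - 0.159)/0.841 = 0.54.

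| Assumed baseline (mean, SD) | 30% fall | 40% fall | 50% fall |
|---|---|---|---|
| 80, 20 | 54% | 81% | 97% |
| 90, 20 | 37% | 67% | 93% |
| 100, 25 | 24% | 47% | 78% |

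**3. Noise with no true change.** Assume a within-person CV of 4-8% on both samples. For a participant screened at b, P(Visit 3 < 60) = Φ(ln(60/b)/(√2·CV)). This gives 39-44% at b = 61 and 8-24% at b = 65. Few participants are that close to the limit: under the three distributions, 3-8% lie between 60 and 65, and 0.6-1.8% between 60 and 61.2. I simulated a true value from each distribution with log-normal noise on both samples, keeping those screened above 60. Overall, noise flags about 2-4% for N(80,20), 1-2% for N(90,20) and 0.6-1.3% for N(100,25). Across 32 participants that is 0.2 to 1.3 flags.

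**4. What a 25% row would add.** Since 0.75b < 60 whenever b < 80, the bands already catch every 25% fall from below 80. The added row therefore acts only from 80 upward. It would count 90 to 67.5, 100 to 75 and 120 to 90, none of which is counted now. Using the formula in step 2 with u = 80, 59-83% of participants would start at 80 or above (1 - 0.41 for N(80,20); 1 - 0.17 for N(100,25)). Noise alone would trigger it with probability Φ(ln 0.75/(√2·CV)), at most about 0.55% at CV 8%.

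**The case against.** **The data are not lost.** This stands. SAP 9 requires minimum and maximum for continuous variables, and SAP 12.5 and 12.7 apply value and change from baseline to chemistry by dose. The largest individual fall in each group is therefore the minimum change printed in Table 7.2. Listing 16.2.15 gives individual results, and Protocol 8.1.4 has investigators record clinically significant laboratory changes as adverse events. One affected participant is diluted in a group mean but remains visible in that minimum.

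**The SAP does not contradict itself.** A reader might infer from the haemoglobin comment that it does. The comment sits in the haemoglobin row only, and all five chemistry rows are absolute. Haemoglobin is the only parameter with a standalone change criterion; elsewhere change counts only together with an absolute limit. PR above 200 and QRS above 110 count without any change, as clearance below 60 does. PCSA limits are the sponsor's to define. The comparison shows that a change criterion would fit the table, not that a rule was broken.

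**The count does not miss most large falls.** A reader might infer this from the 50% entry in the first table. A halving escapes only from a baseline of 120 or more, and under the assumed distributions it is counted in 78-97%. Most participants are missed only for falls of about 30% with the two higher assumed baselines, or 40% with the highest.

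**Noise does not dominate.** The high rates at 61 and 65 apply to few participants; the overall rate is about 0.6-4%.

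**Tightening the existing flag would cost something.** One might also require a 25% fall before a crossing of 60 counts. That would remove present flags: 75 to 58 (17/75 = 23%) counts now and would not then. The documents give no reason to prefer that trade.

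**The clinical link is indirect.** The mention of dehydration in Protocol 2.3 concerns overdose, and renal function is not among the listed DLTs (4.6.1) or AESIs (8.2.6).

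**Conclusion.** The point holds for the PCSA count and percentage, which are stated components of a primary endpoint, and no further. The same relative loss is scored differently according to entry clearance. For falls of about 30-40% the difference is large enough that a dose-level PCSA percentage should not be read alone as evidence for or against a renal effect. The uncounted falls in step 1 follow from the text. The shares in step 2 rest on assumed baselines and the noise rates also on an assumed CV; neither has a source in the documents. The documents do not support saying that renal falls are hidden or that the flag is mostly noise. This is worth correcting because the data already exist and the change is small.

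**What to change.** In SAP 19, add a separate creatinine clearance row: decrease from baseline of at least 25%. This is the relative size the table already uses for PR and QRS; the sponsor may fix another value before unblinding. Report it in Tables 7.2 and 7.2.1 beside the absolute bands, and leave those bands counted as they are.

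Cost: one extra row in SAP 19 and in the two tables, with no new data. The downside is one more threshold to settle before unblinding, and 25% has no renal source in the documents. If unblinding has already occurred, report the row as a post-hoc analysis, identified as SAP 6.2 requires.

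Limit: chemistry has one scheduled post-dose sample, at Visit 3 (D8 ± 2 days). No threshold can recover a transient fall that has resolved by then.
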